6. DOSAGE AND ADMINISTRATION

The study drug ALS-008176 will be provided as tablets for oral administration. Study drug administration should start as soon as possible, but no later than 4 hours after randomization in

order to maximize the opportunity for the compound to inhibit viral replication and potentially improve outcomes.

Subjects will be dosed with a single LD followed by 9 MDs twice daily (at least 8 hours apart and maximum 16 hours apart, with no more than 2 doses per calendar day) during Day 1 to Day 5/6 (depending on the timing of the LD administration). In Part 1, subjects will be randomized in a 1:2 ratio to Regimen A or B. In Part 2, subjects will be randomized in a 1:1:1 ratio to Regimen A, B, or C.

	Regimen A^a	Regimen B^a	Regimen C^a
Treatment Regimen	Placebo	Low-dose ALS-008176: 750 mg LD/250 mg MD	High-dose ALS-008176: 1,000 mg LD/500 mg MD
Loading Dose	Placebo: 1 intake of 3 tablets	ALS-008176: 1 intake of 3 x 250 mg tablet	ALS-008176: 1 intake of 2 x 500 mg tablet Placebo: 1 intake of 1 tablet
Maintenance Dose	Placebo: 9 intakes of 1 tablet	ALS-008176: 9 intakes of 1 x 250 mg tablet	ALS-008176: 9 intakes of 1 x 500 mg tablet

^a Placebo tablets will be visually identical to their active drug counterparts.

Administration of each dose should occur at approximately the same time each day. ALS-008176 can be administered without regard to food intake. The date and time of dose administration, the date and time of food intake (limited to the food ingested within 30 minutes before or after study drug administration), and the type of food will be recorded in the eCRF during hospitalization.

In case the subject is discharged prior to the completion of dosing, study drug administration will be continued at home until all doses are administered (Day 5/6), and the date and time of dose administration will be recorded in the electronic device used for eCOA. The investigator/study-site personnel will instruct subjects on how to store the study drug for at-home use as indicated for this protocol.

An overdose in this study is defined as a calculated dose exceeding the planned dose.

7. TREATMENT COMPLIANCE

Study drug will be administered enterally.

In case a dose is missed, the dose may be given up to 6 hours after the scheduled time. If more time has elapsed the dose should be skipped and the next dose should be given at the next scheduled time point per the initial dose schedule.

The investigator/study-site personnel will maintain a log of all study drug administered. Drug supplies for each subject will be inventoried and accounted for.

In the event of the subject being discharged (after Day 2 procedures) from hospital during the dose period, the subject will administer study drug at home and will be required to document the dose of study drug in a study medication log on the electronic device provided during screening.

The subject will receive instructions on compliance with study drug administration at the screening visit. During the course of the study, the investigator or designated study-site personnel will be responsible for providing additional instruction to re-educate any subject who is not able to ensure compliance with the study drug.

8. PRESTUDY AND CONCOMITANT THERAPY

Prestudy therapies administered up to 7 days before first dose of study drug must be recorded at screening.

All subjects will receive supportive care according to local institution standard. While treatment guidelines and standards vary based on local practice and should be considered in the management of subjects, within the parameters of this study, it is recommended that supplemental oxygen can be administered or withdrawn, as appropriate to maintain an SpO₂ ≥93% (for subjects whose baseline SpO₂ is ≥93% when clinically stable).

Concomitant therapies must be recorded throughout the study beginning with start of the first dose of study drug to the Day 28 visit (±2 days). During hospitalization, concomitant medication will be recorded by the site staff in the eCRF. Upon discharge, subjects will be required to document use of concomitant medication in the electronic device in a medication log, which will serve as basis for recording the concomitant medication in the eCRF by the site staff.

Concomitant therapies should also be recorded beyond Day 28 in the subject's medical notes and reported by SAE forms (if applicable) only in conjunction with SAEs that meet the criteria outlined in Section 12.3.2.

All therapies (prescription or over-the-counter medications, including vaccines, vitamins, herbal supplements, home oxygen therapy; non-pharmacologic therapies such as electrical stimulation, acupuncture, special diets, exercise regimens) different from the study drug must be recorded in the eCRF. Recorded information will include a description of the type of the drug/therapy, treatment phase, the dose regimen, route of administration, and its indication. Modification of an effective preexisting chronic therapy should not be made for the explicit purpose of entering a subject into the study, however if a subject has received acute doses of a prohibited drug, switching to an alternative drug chosen at the discretion of the investigator is allowed.

Concomitant medications are permitted as indicated for the management of study subjects with the exception of the medications noted here. The following medications are not permitted during the study and for the time period prior to randomization as noted:

- Moderate/strong inhibitors of OAT3: diclofenac, diflunisal, gemfibrozil, mycophenolic acid, piperacillin, probenecid, and teriflunomide (all within 24 hours prior to randomization until 24 hours after the last dose of ALS-008176).
- P-gp inhibitors and inducers such as, but not limited to: amprenavir, carbamazepine, clotrimazole, dexamethasone, fexofenadine, indinavir, morphine, nelfinavir, phenothiazine, retinoic acid, rifampin, ritonavir, saquinavir, and St John's wort (all within 24 hours prior to randomization (14 days for inducers) until 24 hours after the last dose of ALS-008176).

- Systemic medications (either chronically [more than 14 days] or within 21 days prior to randomization), which are known to modulate the host's immune response or increase viral shedding, such as immunomodulatory therapies, except for systemic corticosteroids as noted below.
- Systemic corticosteroids if used for >7 consecutive days immediately prior to randomization at doses higher than 20 mg/day of prednisone or equivalent. Subjects meeting the eligibility criteria at screening but requiring increased doses of systemic corticosteroids (>20 mg/day of prednisone or equivalent) for a prolonged period (>7 consecutive days) during the study are allowed to continue participating in the study.
- Prescription medications intended to prevent or treat the RSV infection itself (eg, ribavirin, IV immunoglobulin, palivizumab), an investigational drug, an investigational vaccine, or an invasive investigational medical device within 30 days or 5 half-lives (whichever is longer) before the planned first dose of study drug. Prescription medications intended to treat the symptoms/sequelae of the RSV infection are permitted.

The sponsor must be notified in advance (or as soon as possible thereafter) of any instances in which prohibited therapies are administered.

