2.1.2. Endpoints

Primary Endpoints

For Part 1:

The primary endpoint is the PK of ALS-008112 and ALS-008144 (and other metabolites, if applicable) in plasma.

For Part 2:

The primary endpoint is RSV RNA viral load (measured by qRT-PCR in the mid-turbinate nasal swab specimens) AUC from immediately prior to first dose of study drug (baseline) until Day 7.

Secondary Endpoints

The secondary endpoints for Part 1 and Part 2 are:

- Safety/tolerability including AEs, physical examinations, vital signs, ECGs, and clinical laboratory results
- RSV clinical course endpoints:
 - Length of hospital stay from admission to discharge and from study treatment initiation to discharge.
 - Length of hospital stay from admission to readiness for discharge and from study treatment initiation to readiness for discharge, with readiness for discharge defined by the investigator.
 - Need for and duration of intensive care unit (ICU) stay.
 - Need for and duration of supplemental oxygen (regardless of method used).

-
- Number of hours until peripheral capillary oxygen saturation (SpO₂) ≥93% on room air among subjects who were not on supplemental oxygen prior to the onset of respiratory symptoms.
 - Respiratory rate, SpO₂, and body temperature return to pre-RSV disease level.
 - Need for and duration of noninvasive ventilator support (eg, continuous positive airway pressure) and/or invasive ventilator support (eg, endotracheal-mechanical ventilation or mechanical ventilation via tracheostomy).
 - Time to return to pre-RSV functional status (Katz ADL score).
 - Need for hydration and feeding by IV catheter/nasogastric tube.
 - Time to clinical stability defined as the time at which the following criteria are all met:
 - normalization of blood oxygen level (return to baseline; by pulse oximetry) without requirement of supplemental oxygen beyond baseline level
 - normalization of oral feeding
 - normalization of respiratory rate
 - normalization of heart rate
 - Improvement on the ordinal scale.
 - All-cause mortality.
 - RSV RNA viral load as measured by qRT-PCR of the mid-turbinate nasal swab specimens which will be used to determine the following:
 - Viral load over time.
 - Peak viral load, time to peak viral load, rate of decline of viral load, and time to RSV RNA being undetectable.
 - Proportion of subjects with undetectable viral load at each time point.

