
[Time-to-event] (3 separate parameters: overall, invasive, non-invasive)
 
Time to end of supplementation feeding, hydration (hours) [Time-to-event] (2 separate parameters)
	
study drug)/3600, rounded to one decimal
 
The event is defined as the last end date and time of the measured parameter (supplemental oxygen, invasive oxygen, non-invasive oxygen, feeding or hydration). If this date is missing, the end date is considered to be after study completion or withdrawal.
 
Subjects who complete or withdraw from the study prior to the last end date and time of the measured parameter will be censored at the date of completion or withdrawal. If the time is not available they will be censored at 12:00. In case of death prior to the last end date and time of the measured parameter, the time of death will be taken as censoring time (or 12:00 if not available).
 
If no oxygen supplementation, supplemental feeding or hydration was necessary post baseline, the value will be set to 0.

Time point of SpO2 \geq 93% on room air
	
The first time point with SpO2 \geq 93%, where no supplemental oxygen supplementation is given at or after this time point and where no value $<$ 93% are measured after this time point.

Time to SpO2 \geq 93% (hours) on room air [Time-to-event]
	
minimum[date and time of time point with SpO2 \geq 93% on room air, date and time of last SpO2 measurement] - date and time of first dose of study drug)/3600[†], rounded to one decimal
 
Subjects with SpO2$<$93% on room air or who are still on oxygen supplementation at the last SpO2 assessment will be censored at the date and time of the last SpO2 assessment.
 
This parameter will only be calculated for subjects who were not on supplemental oxygen prior to current hospitalization

Time point of return to pre-RSV disease level (hours) for HR, RR, SpO2 (3 separate parameters)
	
The first time point where it is indicated by the investigator that the observed value is normal for the subject, and for none of the time points after this point in time the values are indicated to be abnormal for the subject (separate for HR, RR or SpO2).

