4.3.3. Vital Signs

Systolic and Diastolic blood pressure, pulse rate, respiratory rate, tympanic temperature and oxygen saturation will be investigated.

Definitions

The following abnormalities will be defined:

Abnormality Code	Vital Signs parameter		
	Pulse	DBP	SBP
Abnormalities on actual values			
Abnormally low	< 45 bpm	≤ 50 mmHg	≤ 90 mmHg
Grade 1 or mild	-	> 90 mmHg - < 100 mmHg	> 140 mmHg - < 160 mmHg
Grade 2 or moderate	-	≥ 100 mmHg - < 110 mmHg	≥ 160 mmHg - < 180 mmHg
Grade 3 or severe	-	≥ 110 mmHg	≥ 180 mmHg
Abnormally high	≥ 120 bpm	-	-

Abnormality Code	Respiratory
Abnormalities on actual values	
Normal	< 17 breaths per minute

Abnormality Code	Respiratory
Grade 1 or mild	17-20 breaths per minute
Grade 2 or moderate	21-25 breaths per minute
Grade 3 or severe	> 25 breaths per minute
Grade 4 or potentially life threatening	intubation-

Abnormality Code	Tympanic Temperature (°C)
Abnormalities on actual values	
Normal	< 37.5
Abnormally high	≥ 37.5

Abnormality Code	Oxygen Saturation (%)
Abnormalities on actual values	
Abnormally low	< 95
Normal	≥ 95

In determining the abnormalities, the following rules are applied:

- worst grades/abnormalities are determined over the whole observational period for each trial phase separately, including post-baseline scheduled and unscheduled measurements of that phase.
- The abnormalities ‘abnormally low’ and ‘abnormally high’ /grades are considered equally important, i.e. if a subject has as well an abnormally low as an abnormally high or graded value post-baseline, both abnormalities are shown in the tables. (This means that the sum of the percentages can be more than 100%)

An abnormality will be considered treatment-emergent in a particular phase if it is worse than baseline. If baseline is missing, the abnormality is always considered as treatment-emergent. A shift from ‘abnormally low’ at baseline to ‘abnormally high’ or ‘grade ...’ post baseline (or vice versa) is also treatment-emergent.

Analysis Methods

Actual values and change from baseline will be summarized by treatment group at each scheduled time point. The number and percentage of will be shown in a cross-tabulation of the toxicity/abnormality post-baseline versus baseline at each scheduled time point.

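### The SpO2 safety flag in SAP 4.3.3 (one low category, below 95%, blind to oxygen use) conflicts with the protocol's 93% figure, so it can score weaning to 93–94% as treatment-emergent and miss falls from an already low baseline

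*Protocol*

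**What the plan says.** **Oxygen target.** Protocol Section 8 recommends that "supplemental oxygen can be administered or withdrawn, as appropriate to maintain an SpO₂ ≥93" per cent. It is a recommendation, alongside local standards of care, and it is limited by the words "for subjects whose baseline SpO₂ is ≥93% when clinically stable".

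**Efficacy endpoint.** Protocol 2.1.2 lists "Number of hours until peripheral capillary oxygen saturation (SpO₂) ≥93% on room air" as a secondary endpoint, in subjects not already on supplemental oxygen before the illness. SAP Table 1 (4.2.4.1) makes the event a sustained one: the first such value "where no supplemental oxygen supplementation is given at or after this time point", with no later value below 93%.

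**Safety table.** SAP 4.3.3 adds SpO2 to the safety vital signs: "Systolic and Diastolic blood pressure, pulse rate, respiratory rate, tympanic temperature and oxygen saturation will be investigated". Its oxygen saturation table has two categories, abnormally low (below 95) and normal (95 or above), and does not mention oxygen use. Three rules follow:

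- "An abnormality will be considered treatment-emergent in a particular phase if it is worse than baseline".
- The worst value is taken over each trial phase, including unscheduled readings.
- "If baseline is missing, the abnormality is always considered as treatment-emergent".

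The protocol does not supply the 95% limit. Its vital-sign limits (Attachment 6) cover pulse and blood pressure only. Neither document explains why the two figures differ.

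**The concern.** A value of 93% or 94% is within the recommended target in one place, can be the efficacy event in another, and is an abnormality in the safety table. More important than the two numbers is that the flag compares readings without regard to oxygen. Baseline is the last record before first intake (SAP 2.1), whether on oxygen or room air. Coming off oxygen is recovery, yet it can lower the reading from the normal to the low category and so be tabulated as worsening.

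The single category also fails in the other direction. Once a subject is below 95% at baseline, no further fall changes the category, so the fall cannot be worse than baseline under the rule. In adults hospitalized with a respiratory infection, that is the change a safety table should show.

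At stake is how the low-SpO2 rows are read by arm. Time on oxygen is itself an outcome that treatment may alter, so an arm weaned sooner could show more flags.

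**Working it through.** The plan gives no figure to reproduce here. The check applies the stated rule.

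**Step 1. The rule.** A post-baseline value p is low if p < 95. It is treatment-emergent if it is low and baseline b is either 95 or above, or missing.

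| Baseline SpO2 | Later 93 or 94 | Later 92 | Later 95 or 96 |
|---|---|---|---|
| 95, 96 or 98 | treatment-emergent | treatment-emergent | not flagged |
| missing | treatment-emergent | treatment-emergent | not flagged |
| 90, 92, 93 or 94 | low, not treatment-emergent | low, not treatment-emergent | not flagged |

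The 98 → 94 case is the weaning problem when 98 was measured on oxygen and 94 on room air. The 94 → 92 case is the missed fall, and the result is the same however far the later value drops. The worst-abnormality counts in SAP 4.3.3 also include every low reading, whatever the baseline.

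**Step 2. Same rule with the cut at 93%.** No reading of 93 or 94 is flagged for any baseline, including a missing one, and a move from 93 or 94 to 92 becomes treatment-emergent. This checks consistency with the protocol's figure. It does not show which threshold is clinically right.

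**Step 3. One reading is enough.** SpO2 is read every 4 hours in hospital through Day 7 (Time and Events Schedule), so 6 times a day. If each reading independently has chance q of being 93–94% (q is assumed), the chance of at least one in n readings is 1 − (1 − q)^n.

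| Days in hospital | n | q = 1% | q = 5% | q = 10% |
|---|---|---|---|---|
| 2 | 12 | 11% | 46% | 72% |
| 5 | 30 | 26% | 79% | 96% |
| 7 | 42 | 34% | 88% | 99% |

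For example, 1 − 0.95^12 = 0.46.

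**Step 4. Illustration with the baseline condition.** All inputs are assumptions: subject means centred on 95 or 96, between-subject SD 1 or 1.5, within-subject SD 1, one baseline reading, 12 or 24 later readings, values rounded to whole per cent, 200,000 simulated subjects per setting, and no weaning effect. Across the eight settings:

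- 53–90% of subjects have at least one reading below 95%, and 5–36% have one below 93%.
- 34–54% are treatment-emergent at the 95% limit. Of these, 80–94% never fall below 93%.
- Of subjects who do fall below 93%, 53–80% are not treatment-emergent, because their baseline was already below 95%.

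These figures show that both failures can be common under plausible inputs. They do not estimate what the trial would show.

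**The case against.** **A care target and a screening flag need not share a number.** This is fair, and the SAP does the same elsewhere: a tympanic temperature of 37.5 °C or more is abnormally high in 4.3.3, while the efficacy definition accepts up to 37.8 °C. The different number alone would be a minor wording matter. What remains is that the SpO2 flag also ignores oxygen status, which the recommendation expects to change during the stay.

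**Desaturation is visible elsewhere.** This stands. SAP 4.3.3 also summarises actual values and changes from baseline and lists abnormal values. Other sections analyse time to 93% on room air, return to the pre-RSV SpO2 level, and need for and duration of oxygen, and tabulate respiratory failure. A reader might infer that falls below 93% are lost from the analysis. They are not; they are only missed or diluted in this flag.

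**Only descriptive tables are touched.** This also stands. Protocol 11.10 plans no statistical testing of safety data, the primary endpoint is unaffected, and the discontinuation criteria in 9.7.1 and 10.2 do not use the flag. One cut-off for all arms is a weaker defence, because the flag depends on oxygen withdrawal, which can differ by arm. Whether it would differ is conjecture.

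**Requiring a baseline at the same oxygen status could backfire.** This is correct. A subject on oxygen at baseline may have no room-air baseline, and the missing-baseline rule would then flag every low room-air value. The fix has to avoid this.

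**Conclusion.** The conflict is real and limited. A subject is wrongly shown as worsening if baseline was 95% or above on oxygen and the value settles at 93–94% after weaning. A missing baseline has the same result. A subject already below 95% at baseline who falls well below 93% is never treatment-emergent. Both results follow from the stated rule without any assumption.

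Two stronger readings are tempting and are not supported:

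- That patients weaned as recommended are in general scored as treatment-emergent. Those with a baseline below 95%, and those who stay at 95% or above, are not. The 93% target is itself conditional.
- That the table mostly counts patients managed to the target. The documents give no SpO2 distribution, so the share affected cannot be computed, and the percentages in the working rest wholly on assumed inputs.

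Nor is every 93–94% reading an efficacy success: the event must be sustained off oxygen, in a subject not previously on it. The consequence is misleading rows in descriptive safety tables and listings. That is worth correcting before database lock, but it does not threaten the trial's main conclusions.

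**What to change.** Reconcile Protocol Section 8, the room-air endpoint (Protocol 2.1.2, SAP Table 1) and SAP 4.3.3 through the SAP table:

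1. Split the low category at the protocol's own figure: 93–94% and below 93%. A fall from the first to the second then counts as worse than baseline. A baseline already below 93% still cannot worsen by category; the existing change-from-baseline summaries and listings cover that case.
2. Tabulate and list each flag by oxygen status (room air or on oxygen) at baseline and at the reading.
3. Where the two differ, show the value in a separate row for changed oxygen status, with the direction of change. Do not count it as treatment-emergent, and do not apply the missing-baseline rule to it.
4. Take the worst value separately for unchanged-status and changed-status readings, so that one does not mask the other.

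SpO2 and the type, duration and amount of oxygen are already collected, and SAP Table 1 already uses oxygen start and end times. The cost is a few lines of SAP text, some programming and slightly longer tables. This is an analysis definition; it does not say which saturation level is clinically right and changes nothing in patient management.

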9. STUDY EVALUATIONS

9.1. Study Procedures

9.1.1. Overview

The [Time and Events Schedule](#) summarizes the frequency and timing of efficacy, PK, medical resource utilization, health economic, biomarker, and safety measurements applicable to this study.

Repeat or unscheduled samples may be taken for safety reasons or for technical issues with the samples.

The eCOA will be provided to the subject at screening to record the subject's ratings of the severity of the symptoms (RI-PRO), additional questions about health and functioning, and HRQoL (EQ-5D-5L) (see [Attachment 2](#), [Attachment 3](#), and [Attachment 4](#), respectively). The subjects will complete the eCOA once daily throughout the study from screening to Day 28 at approximately the same time each day. The assessment on Day 1 needs to be recorded predose, before the LD. If the screening assessment was performed less than 8 hours prior to the LD, the predose assessment does not need to be performed.

The investigator/study-site personnel will provide sufficient information (included in the study manual) to enable the subject to complete the eCOA and will ensure that the eCOA is completed correctly and on schedule to avoid missing or incorrect data. If the subject is unable to complete the assessment on the device, the subject's spouse, partner, relative, friend or the investigator/study-site personnel trained on the eCOA device can read the questions and responses aloud to the subject and enter the subject's responses in the eCOA device on the subject's behalf using the interview administration procedures explained in the eCOA completion guide. If the subject is too ill at the time the eCOA is scheduled to be administered to

respond to the questions, the subject's spouse, partner, relative, friend, or the investigator/trained study-site personnel should indicate the reason the eCOA was not completed on the eCOA device for that assessment. The investigator/study-site personnel will instruct the subject to complete the eCOA questionnaires and transmit the eCOA data at approximately the same time each day from screening through end of follow-up.

Prior to completing the screening assessment, the subject (or the subject's spouse, partner, relative, or friend on the subject's behalf) must complete a training module (included as part of the eCOA device) on how to enter the subject's responses to questions in the eCOA device. If in the investigator's opinion, the subject (or the subject's spouse, partner, relative, or friend) is unlikely to reliably enter the information in the eCOA device on a daily basis for the duration of the study, the site will retain the eCOA device upon the subject's discharge and arrange for the investigator or trained study-site personnel to interview the subject by phone and record the subject's responses in the eCOA device on the subject's behalf each day post discharge to end of follow-up.

The Katz ADL questionnaire (see [Attachment 5](#)) will be completed by the investigator/study-site personnel after interviewing the subject and the data will be entered into the eCRF by the investigator/study-site personnel. The Katz ADL questionnaire will be completed twice at screening to document retrospectively the subject's pre-RSV infection functional status (ie, prior to first signs/symptoms of RSV) and the subject's current functional status (ie, after the occurrence of RSV signs/symptoms). The Katz ADL questionnaire will be completed once daily for the entire duration of hospitalization and on Day 7, Day 10, Day 14, and Day 28 if the subject is discharged.

If multiple assessments are scheduled for the same time point, it is recommended that procedures be performed in the following sequence: noninvasive procedures should be collected first before invasive procedures (eCOA completion/Katz ADL questionnaire/ECG first, then vital signs/SpO₂, then mid-turbinate nasal swab, with blood draw last). However, mid-turbinate nasal swabs for RSV RNA viral load and blood collections for PK assessments should be kept as close to the specified time as possible. Other measurements may be done earlier than specified time points if needed. Actual dates and times of assessments will be recorded in the source documentation and eCRF.

If treatment duration is extended to up to 10 days, subjects will have an additional clinic visit 1 day (+2 days) after their last dose.

Medical resource utilization and health economics data will be collected. Refer to Section 9.6, for details.

The maximum amount of blood drawn from each subject in this study will not exceed 110 mL.

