4.2.5.1.2. Analysis Methods

Actual values and changes from baseline will be summarized by treatment group at each scheduled time point for the RSV-PRO domain and total scores. Mean \pm SE graphs over time for the actual values and changes from reference will be presented.

Time-to-alleviation will be analyzed in an exploratory sense using a summary table including number of subjects included in the analysis, number of subjects censored, 25th and 75th percentiles and median time to event, with 95% confidence intervals based on log-log transformation method, will be presented. The data will be presented graphically using the Kaplan-Meier estimate of the survival function. For each comparison of active versus placebo the stratified Gehan test will also be presented.

Frequency tabulation of each of the 32 items at the time point of return to return to usual activities and time point of return to usual health as defined in section 4.2.5.2.1.

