4.2.5.2. Adult RSV Additional Questions

4.2.5.2.1. Definition

Table 4. Calculations and Conversion Formulae

Measurement	Formula
Time to return to usual activity	
The time in hours from the first dose of investigational product till the first one of 2 successive cases where the response is ‘Yes’ on RSV-PRO additional question 7 (“have you returned to your usual activities?”) . Time points with missing data are ignored in this analysis. The successive recordings cannot be within the same window. In case there are 2 recordings within a single window (i.e. morning window, afternoon window or evening window) the worst case within that window will be taken.
 
In cases where there are no sufficient recordings, the endpoint will be censored. Censoring will be at time of the last assessment if ticked as “Yes”; otherwise censoring will be the first window after the last assessment (lower limit). One exception is censoring at the Day 28 Visit (last study day for the subject). If the subject is not returned to usual activities/health on this day, the time of the last diary entry will be taken as the time of censoring.

Time to return to usual health	
The time in hours from the first dose of investigational product till the first one of 2 successive cases where the response is ‘Yes’ on RSV-PRO additional question 9 (“have you returned to your usual health?”). Time points with missing data are ignored in this analysis. The successive recordings cannot be within the same window. In case there are 2 recordings within a single window (i.e. morning window, afternoon window or evening window) the worst case within that window will be taken.
 
In cases where there are no sufficient recordings, the endpoint will be censored. Censoring will be at time of the last assessment if

	both items are ticked as “Yes”; otherwise censoring will be the first window after the last assessment (lower limit). One exception is censoring at the Day 28 Visit (last study day for the subject). If the subject is not returned to usual activities/health on this day, the time of the last diary entry will be taken as the time of censoring.
Time to full recovery	The maximum of the time to return to usual activity and usual health when both have an event, or the minimum of censored time(s) if at least one is censored.

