4.2.5.2.2. Analysis Methods

Time to return to usual activity and usual health

Kaplan-Meier curves will be provided by treatment group. For each comparison of an active group versus placebo the stratified Gehan test will also be presented.

Other RSV additional questions

The number and percentage of subjects per category will be tabulated over time by treatment group for items 1 to 6 and item 8 of the RSV additional questions.

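### Return to usual activity and usual health: a day missed because the subject was too ill to answer is skipped, so it does not break a run of 'Yes' answers as a 'No' would

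*Protocol*

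**What the plan says.** Protocol 9.1.1 sets the schedule: "The subjects will complete the eCOA once daily throughout the study from screening to Day 28 at approximately the same time each day". A relative, friend or staff member may read out the questions and enter the answers for a subject who cannot use the device. For the subject who cannot answer at all, the instruction begins "If the subject is too ill at the time the eCOA is scheduled to be administered to" respond, and the helper or staff member "should indicate the reason the eCOA was not completed on the eCOA device for that assessment".

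SAP 4.2.5.2.1, Table 4, defines time to return to usual activity (additional question 7) and to usual health (question 9). Each runs from first dose "till the first one of 2 successive cases where the response is" 'Yes'. The missing-data rule is one sentence: "Time points with missing data are ignored in this analysis". It does not distinguish reasons and does not limit the gap between the two answers. If a pair never occurs, "In cases where there are no sufficient recordings, the endpoint will be censored". Time to full recovery is the later of the two times when both are events.

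The other questionnaire outputs are by-day summaries. For the symptom scores, "Actual values and changes from baseline will be summarized by treatment group at each scheduled time point for the RSV-PRO domain and total scores"; for the additional-question responses, "The number and percentage of subjects per category will be tabulated over time by treatment group for items 1 to 6 and item 8". No imputation rule is given for them. I found no place in the SAP that uses the recorded reason for non-completion.

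**The concern.** Requiring two successive 'Yes' answers appears intended to exclude a single good day followed by a setback. Skipping a day missed for an unrelated reason, such as a device fault, is reasonable because that day says nothing about recovery. A day on which the subject was too ill to respond does: the subject had not returned to usual activities or usual health. Skipping it treats the worst possible day as no information, so a subject too ill to answer gets an earlier recovery time than one who was well enough to answer 'No'.

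At stake are the Kaplan-Meier curves and the stratified Gehan tests of each active arm against placebo (SAP 4.2.5.2.2), time to full recovery, and the tabulation of the 32 symptom items at the time of return (SAP 4.2.5.1.2), which would be read on the wrong day.

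**Working it through.** The documents give no rate of too-ill days and no planned effect for these endpoints, so there is no stated figure to reproduce. The check applies the Table 4 rule to sequences of daily answers.

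**Rule as written:** delete missing days, then take the first 'Yes' whose next remaining answer is also 'Yes'. **Comparison rule:** score a too-ill day as 'No', then do the same. Days count from first dose; Y = Yes, N = No, I = too ill.

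| Sequence | As written | Too ill = 'No' | Shift |
|---|---|---|---|
| N to Day 7, then Y I Y Y (Days 8-11) | Day 8 | Day 10 | 10 - 8 = 2 days |
| N to Day 7, then Y I Y (last answer Day 10) | Day 8 | no event, censored | event lost |
| N to Day 5, Y, five I, Y Y | Day 6 | Day 12 | 12 - 6 = 6 days |
| N to Day 5, Y, five I, Y (last answer) | Day 6 | no event, censored | event lost |
| N to Day 5, Y, five N, Y Y | Day 12 | Day 12 | none |
| I on Days 3-5, N on Days 6-7, Y Y | Day 8 | Day 8 | none |

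The third and fifth rows differ only in whether the five bad days were unanswerable or answered 'No'. The written rule gives Day 6 for the first and Day 12 for the second. The last row shows that too-ill days before any 'Yes' do no harm.

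**Illustrative frequency (all inputs assumed).** 20,000 subjects were simulated per setting over 28 daily answers, with these inputs:
- 10% daily chance of a first 'Yes';
- 2%, 5% or 10% daily chance of relapse while at 'Yes';
- 40% daily chance of returning to 'Yes' after relapse;
- 25%, 50% or 100% of relapse days missed as too ill, the rest answered 'No'.

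The share of events bridged across a too-ill gap ran from 0.2% (2% relapse, 25% missed) to 9.4% (10% relapse, all missed). Where both rules gave an event, the written rule was early by 2.4 to 3.8 days on average. About 94% of simulated subjects had an event, so with 30 per arm this is 30 x 0.94 x 0.002 = 0.06 to 30 x 0.94 x 0.094 = 2.7 subjects per arm. The upper end needs every relapse day to be unanswerable.

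**The case against.** The strongest objection is that the sequence is rare. The subject must report a return, become too ill to answer even with a helper reading the questions, and then report a return again. ICU and intubated days mostly come before any first 'Yes', where skipping them changes nothing. This stands, and it keeps the point small.

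Relapse is also visible elsewhere. Re-hospitalization for the same RSV disease is an SAE, respiratory readmission is tabulated, and ICU stay, oxygen use, mortality and the ordinal scale do not depend on the subject completing the questionnaire. This stands too: the defect misdates these recovery times but does not hide relapse from the trial.

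A reader might go further and infer that the by-day symptom and quality-of-life means favour the arm with more subjects too ill to answer. With no imputation rule, those means appear to describe responders only, and under assumed shares of 2-20% too ill and a true gap of 0.5-2 points on the 0-4 scale, one arm's mean severity would be understated by 0.02 x 0.5 = 0.01 to 0.20 x 2 = 0.40 points. But the documents give no shares by arm, so neither direction nor size of a between-arm bias can be stated. SAP 2.4 already shows the number of observations with each mean.

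A reader might also want 'too ill' ranked as the worst category in the tables. That does not follow: a stable ventilated subject is not below 'much worse' than yesterday (question 5), and being unable to answer is not worse than extreme pain on the EQ-5D.

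Finally, the protocol asks for a reason but shows no coded list, so whether 'too ill' is stored in analysable form needs confirming.

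**Conclusion.** The point holds for the definition in SAP Table 4. As written, a documented too-ill day between two 'Yes' answers produces an earlier event than a 'No' would, and can create an event where none would be confirmed. This follows from the rule itself and needs no assumption. The two-day shift in the Day 8 example does need the further 'Yes' on Day 11.

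Only time to return to usual activity, time to return to usual health, time to full recovery and outputs built on them are affected. The symptom alleviation times in SAP Table 3 use a single qualifying day and cannot be bridged. All of these are exploratory; the primary viral load AUC, its type 1 error and its power are untouched. The documents show that the rule permits bridging, not that it will happen often. The frequency is likely low, and the figures above are assumptions. This is a minor, worthwhile correction.

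**What to change.** In SAP Table 4, for questions 7 and 9, state that a day documented as too ill to respond counts as 'No' (not returned) and breaks a 'Yes' run, and that only days missing for other reasons, or with no reason recorded, are skipped. Time to full recovery then needs no separate change.

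Optionally, show the number too ill by arm and day beside the RSV-PRO and EQ-5D summaries. This is a caution for the reader and does not correct the means.

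The cost is a line of SAP text and a small programming change. No new data collection is needed, provided the device stores the reason in usable form; if it is free text, a blinded review before database lock can classify it. The change should be made before unblinding so that it is not a post hoc choice.
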